4.4 Study Visits

Cohort 1:

- Week 0: enrollment visit
- Weeks 2 and 4: oral phase safety visits
- Week 5: the first injection visit
- Weeks 6, 9, 13: safety visits after the 1st injection
- Week 17: the second injection visit
- Weeks 18 and 23: safety visits after the 2nd injection
- Week 29: the third injection
- Weeks 30, and 35: safety visits after the 3rd injection
- Week 41: primary endpoint visit
- Weeks 53, 65, 77, 89, 101: tail phase safety visit
- Week 105: final study visit.

Cohort 2:

- Week 0: enrollment visit
- Weeks 2 and 4: oral phase safety visits
- Week 5: the first injection visit
- Week 6: safety visits after the 1st injection
- Week 9: the second injection visit
- Weeks 10 and 13: safety visits after the 2nd injection
- Week 17: the third injection visit
- Weeks 18 and 21: safety visits after the 3rd injection
- Week 25: the forth injection
- Weeks 26, and 29: safety visits after the 4th injection
- Week 33: the fifth injection visit
- Week 34 and 37: safety visits after the 5th injection
- Week 41: primary endpoint visit
- Weeks 53, 65, 77, 89, 101: tail phase safety visit
- Week 109: final study visit.

4.5 Allowable Visit Windows

The allowable visit windows for all visits, including injection visits, are outlined in Section 12 Data Management of SSP Manual. The allowable visit windows are pre-specified around the targeted visit windows. If a participant is unable to report to the visit during this time frame, or if a participant misses his/her appointment within the visit time frame, the CMC must be contacted for consultation regarding whether rescheduling outside of the visit window is allowable. Visits that occur outside of the allowable visit windows are coded either late or early.

4.6 Study Sites

HIV Prevention Trials Network (HPTN)-affiliated Clinical Trial Units (CTUs) and/or Clinical Research Sites (CRSs) participating in this study is listed in the SSP Manual, and include sites in Brazil, sub-Saharan Africa (SSA), and the United States (US).

4.7 Randomization

Enrolled participants are randomized to one of two study arms with an active GSK1265744 to placebo ratio of 3:1 in two cohorts. The arm randomization is stratified by

gender and region (US and non-US sites) and done in blocks to ensure balanced treatment assignments within each gender and region (US and non-US). The randomization scheme is generated, operationalized and maintained by HPTN SDMC using Frontier Science & Technology Research Foundation, Inc. (FSTRF) system. Additional details regarding the process of randomization are included in the SSP Manual.

4.8 Blinding

Study site staff, with the exception of the site Pharmacist of Record or their designee, and participants will be blinded to the random assignments. Blinding will be maintained until the last participant enrolled in to the active drug arm in cohort 2 has completed their Week 41 visit (the time point of the primary endpoint of the study), and when all data related to the Week 41 visit has been entered into the database, as well as cleaned and verified. At a specified time directed by the HPTN SDMC, participants will be unblinded to their treatment assignment, and participants in the placebo arm will no longer need to be followed. Participants in the active study product arm will continued to be followed for 52 weeks after their last injection.

5 PLANNED ANALYSES

5.1 SMC Report

The HPTN Study Monitoring Committee (SMC) will be utilized in this study to ensure objective medical and/or statistical review of safety issues in order to protect the ethical and safety interests of participants and to protect the scientific validity of the study. The SMC will conduct interim reviews of the study data approximately every 6 months. Study data including rates of subject accrual, visit retention, progression of primary and main secondary endpoint assessments, data collection and laboratory issues will be shared by the study team with the SMC in an open session. In a closed report, safety data by unblinded treatment arm will be provided to the SMC by HPTN SDMC in the closed report.

The first SMC review will be conducted when approximately 50% of the subjects complete Week 17 (second injection) and at least every six months thereafter.

5.2 Interim Analysis

An interim analysis will be performed when 50% of the participants have completed their primary endpoint visit (Week 41). All data available at that time will be included in the analysis. Pharmacokinetic data will be analyzed when approximately 50% of Cohort 1 reaches Week 29 (two troughs) for Cohort 1 participants, and when approximately 50% of Cohort 2 reaches Week 17 (two troughs) for Cohort 2.

With the approval from HPTN SMC, the unblinded summaries of the safety and pharmacokinetic data from the analysis may also be provided to the key members of the protocol team and possibly to regulatory agencies to facilitate an initiation of a phase III trial. All members of the protocol team, including GSK and ViiV Healthcare, as well as study participants will remain blinded to individual participant treatment assignment. The data from this analysis may also be combined with the interim data from a similar study being conducted by GSK/ViiV, if needed and appropriate. Pooled summaries will also be provided to the study team to share with regulators.

To maintain the integrity of the clinical study, only the following staff may be unblinded at these SMC interim analyses, as deemed necessary by the SMC: selected clinical

pharmacometrist, programmer, and statisticians who will use unblinded 744 concentrations to build the population PK models, and staff who will incorporate safety data from this analysis into regulatory documents for other studies of 744. The primary study team (medical monitor, clinical study team leader, operational scientist, data manager) should remain blinded until all subjects complete the week 41 visit and the data has been entered and cleaned and all major protocol violators have been identified. The primary study team will only receive unblinded summary tables and figures for the planned interim analysis.

5.3 Primary Analysis

A clinical database will be authorized and released for reporting on the unblinded 41-week safety and tolerability results that encompass the primary endpoints of this study. These findings will be used for internal decision making, possible reporting at scientific meetings, and as needed for regulatory submissions.

5.4 Final Analysis

The final planned analyses will be performed after all participants have completed the follow-up phase and after database freeze.

6 STUDY POPULATIONS

The data collected from the enrolled participants will be analyzed according to the actual treatment that the participants have received. A subset of the enrolled participants might be evaluated in some analyses. For instance, in the primary safety analysis, the safety data from the participants who have completed at least one injection will be analyzed. We define this subset of the enrolled participants as the Injectable/Primary Safety Population below in Section 6.4.

6.1 Screened Population

The Screened Population will consist of all participants who are screened for inclusion in the study.

6.2 Randomized Population

The Randomized Population will consist of all participants who meet the study criteria and are randomly assigned to a treatment in the study at the enrollment date.

6.3 Safety Population

The Safety Population will consist of the participants who are enrolled in the study and have received at least one dose of the study product. In the analyses, the participants will be grouped based on the initial randomization assignments regardless how many doses of the study product they have received.

6.4 Primary/Injectable Safety Population

The Primary/Injectable Safety Population is a subset of the Safety Population that consists of the participants who have received at least one injection of study product. In the analyses, the participants will be grouped based on the initial randomization assignment regardless how many injections they have received.

6.5 Pharmacokinetic Concentration Population

The Pharmacokinetic Concentration Population will consist of the participants in the Injectable Safety Population who have plasma sample(s) collected for PK assay.

6.6 Pharmacokinetic Parameter Population

The Pharmacokinetic Parameter Population will consist of the participants in the Injectable Population who are also assigned to receive the 744 study product and have available samples for PK assay.

6.7 Pharmacogenomic Population

The Pharmacogenomic Population will be determined later.

7 ASSESSMENT WINDOWS

7.1 Treatment Periods

Adverse events, laboratory, vital signs and liver events will be assessed and denoted within the treatment periods that are defined below.

Oral Phase is defined as the time between the enrollment date (Week 0) and the day of the 1st injection (Week 5) or the day of withdrawal, whichever comes first.

Injection Phase is defined as the time between the first injection and the 12 weeks visit after the last injection. For the participants who complete all three injections, the injection phase assessment window is the time between Week 5 and Week 41 visits. For the participants who complete the two injections, the injection phase assessment window is the time between Week 5 visit and Week 29 visit. For the participants who complete only the first injection, the injection phase assessment window is the time between Week 5 visit and Week 17 visit.

Tail Phase is defined as the time between Week 41 to Week 105/109 for ITT analysis. However, for per protocol analysis such as pharmacokinetics analysis, for the participants who did not complete full injections (3 injections for cohort 1 and 5 injections for cohort 2), the tail phase assessment window starts at the 12th (the 8th) weeks after the last injection for cohort 1 (cohort 2) to the last follow-up visit.

On-Treatment is defined as the time between the beginning of the oral phase and the end of the follow-up phase (from the participants' enrollment day to the participants' last day subject's last day in the study).

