10.2 Safety Tables and Graphs (SMC Close Report)

10.2.1 List of Tables

- Permanent discontinuation of study regimen during the oral phase (Weeks 0-5) by treatment arm
- Permanent discontinuation of study regimen during the injection phase (Weeks 5-41) by treatment arm
- Permanent discontinuation of study regimen during the tail phase (Weeks 41-105/109) by treatment arm
- List of early discontinuation of study regimen (reason, study week)
- Grade 3 or higher adverse events by treatment arm during the oral phase (Weeks 0-5)
- Proportion of Grade 2 or higher adverse events by treatment arm during the oral phase (Weeks 0-5)
- Adverse events by severity and relationship to study product during the oral phase (Weeks 0-5)

- Adverse events by MedDRA preferred term ordered by system organ class during the oral phase by treatment arm (Weeks 0-5)
- listing of Grade 3 or above adverse events during the oral phase by treatment arm (Weeks 0-5) with details of the events including severity, relationship to the study product, on-set date, outcome, duration, the enrollment date and days since the enrollment.
- Grade 1 or above AST/ALT by treatment arm during the oral phase (Weeks 0-5)
- Grade 2 or higher adverse events by treatment arm during the injection phase (Weeks 5-41)
- Number and percentage of adverse events by severity and relationship to study product during the injection phase (Weeks 5-41)
- Adverse events by MedDRA preferred term ordered by system organ class during the injection phase (Weeks 5-41)
- Injection site reaction (ISR) adverse events during the injection phase by BMI (above/below median BMI) (Weeks 5-41)
- Grade 1 or above AST/ALT by treatment arm during the injection phase (Weeks 5-41)
- Adverse events by MedDRA preferred term ordered by system organ class during the injection phase (Weeks 5-105/109)
- listing of Grade 3 or above adverse events during the whole injection phase (Weeks 5-81) with details of the events including severity, relationship to the study product, on-set date, outcome, duration, last injection date, and the number of injections prior to the event
- Adverse events by severity and relationship to study product and treatment arm during the whole injection phase (Weeks 5-105/109)
- Grade 1 or above AST/ALT by treatment arm during the whole injection phase (Weeks 5-105/109)
- HIV infection status by study arm
-

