11.2 Safety and Tolerability Analysis

11.2.1 Lists of Tables

Table 8 Permanent discontinuation of study regimen by treatment arm (a) during the oral phase, (b) during the injection phase, and (c) during the on-treatment

Table 9 Adverse experiences by MedDRA preferred term and severity (ordered by system organ class) (a) during the oral phase, (b) during the injection phase, (c) during the tail phase, and (d) during the on-treatment

Table 10 Adverse experiences by MedDRA preferred term and severity – including severe, potential life-threatening or fatal events only (a) during the oral phase, (b) during the injection phase, (c) during the tail phase, and (d) during the on-treatment

Table 11 Adverse experiences by MedDRA preferred term and relationship to study product (a) during the oral phase, (b) during the injection phase, (c) during the tail phase, and (d) during the on-treatment

Table 12 Elevation of liver chemistry and other lab test events (a) during the oral phase, (b) during the injection phase, (c) during the tail phase, and (d) during the on-treatment

Table 13 Summary of Injection Site Reaction Characteristics

Table 14 Summary of characteristics of common ISR symptoms

Table 15 Summary of change in laboratory test at follow up from baseline by visit and cohort

Table 16 Summary of ECG values by treatment arm and visit

Table 17 Summary of maximum change in corrected QTc intervals by category for change from baseline

Table 18 Listing of expedited adverse events (EAE) or serious adverse events (SAE) with the details of the events including severity, relationship to study product, time between onset and last injection, number of injections received (if the events occurring after the 1st injection), and a summary of the event

Table 19 Proportion of participants experiencing any Grade 2 or higher clinical AEs and laboratory abnormalities that occur (a) during the oral phase, (b) during the injection phase (c) during the tail phase, and (d) during the on-treatment period

Table 20 The proportion of participants who discontinue the study product for reasons of toxicity, tolerability, or acceptability (a) prior to completion of the full oral phase and (b) prior to completion of the full injection phase.

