Appendix

Definition of Derived Variables and Study Populations

Study Populations:

Randomized population: randomized=1 if Screnr = 1 (Form SO-1 006, screening outcome)

Oral safety analysis population: randomized=1 and PCpdn>0 and PCpbrp="No", or PCpdn>Pcnumpil if PCpbrp="Yes" (Form PC-1 134, Pill count)

Primary/Injectable safety analysis population: randomized=1 and Iaingiv=1 for week5 (Form IA-1 126, Injection administration)

Derived Variables:

BMI=weight (in kg)/ height(in cm)*height(in cm) (Form LLR-1152, Local Laboratory Results)

Algorithm of defining the phase for AEs

The phase (oral or injection) of AEs was determined based on the AE on-set date and the first injection date as follows.

For AEs with a complete onset date (no missing on day, month, or year)

1. If the AE onset date is before of the first injection date, then the phase of the AE is oral.
2. If the AE onset date is after the first injection date, then phase of the AE is injection.
3. If the AE onset date is on the same date as the first injection date, then:
 - a. If the AE is Injection site reaction, then the phase of the AE is injection.
 - b. If the AE is not Injection site reaction, then the phase is oral.

For the AEs with an incomplete onset date (missing day, day is not mandated)

1. If the onset date is before the first injection date determined by the month and the year of the onset date, then the phase is oral.
2. If the onset date of the AE is after of the first injection date determined by the month and the year of the onset date, then the phase is injection.
3. If the month and year in the AE onset date match to the month and year in the first injection date, then:
 - a. the sites determined whether the AE occurred before or after the first injection.
 - b. If the sites could not determine, PI determined which phase the AE should be.

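### For early injection stoppers, Section 7.1 leaves an interval in neither the injection nor the ITT tail phase, while the appendix algorithm and the SMC tables call it injection phase

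*SAP*

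**What the plan says.** Section 7.1 sets the periods within which adverse events are to be classified. "Injection Phase is defined as the time between the first injection and the 12 weeks visit after the last injection". It then works this out for incomplete courses: after two injections, "the injection phase assessment window is the time between Week 5 visit and Week 29 visit"; for those who "complete only the first injection, the injection phase assessment window is the time between Week 5 visit and Week 17 visit". These examples fit the three-injection schedule of Cohort 1 only.

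The tail is anchored differently: "Tail Phase is defined as the time between Week 41 to Week 105/109 for ITT analysis". A tail that starts 12 weeks (Cohort 1) or 8 weeks (Cohort 2) after the last injection appears in the same paragraph, but only for per-protocol work, with pharmacokinetics as the example. A fourth period, On-Treatment, runs from enrolment to the last day in the study.

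Four other places depend on these boundaries:

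- Section 9.5.5 ends the primary safety window 12 weeks after the last injection in Cohort 1 and 8 weeks after it in Cohort 2. Section 3.1 gives 12 weeks without distinguishing cohorts.
- The appendix algorithm assigns AEs to oral or injection only: "If the AE onset date is after the first injection date, then phase of the AE is injection". It has no end date and no tail category.
- Section 10.2.1 (SMC closed report) lists "Grade 2 or higher adverse events by treatment arm during the injection phase (Weeks 5-41") as a fixed window. It also uses a whole injection phase running to Week 105/109 and, in one listing, to Week 81.
- Section 11.2.1 reports Table 19 for the oral phase and then "b) during the injection phase (c) during the tail phase, and (d) during the on-treatment period", and Tables 9-12 in the same four parts. It does not say which phase rule applies.

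**The concern.** One boundary moves with the participant and the next is fixed, so the two meet only for someone who completes the course. Everyone who stops injections early has an interval between them. Those who stopped for an AE or intolerance are in this group, so the by-phase tables lose information on people whose safety record matters.

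The other rules in the SAP do not lose these events; they put them in a different column. Two programmers who each follow a written rule could produce different injection-phase counts from the same data. The SMC closed report and the final report could likewise show different figures under the same phase name. The appendix, as the only operational AE-phase rule, would if taken literally also label genuine tail events as injection phase, against the window in Section 9.5.5.

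**Working it through.** **Inputs.** Injection weeks from Section 2.3: Cohort 1 at 5, 17, 29; Cohort 2 at 5, 9, 17, 25, 33. Injection-phase length: 12 weeks after the last injection (7.1, general rule), or 8 weeks for Cohort 2 (9.5.5). ITT tail start: Week 41 (7.1). Arm sizes from Section 2.4: Cohort 1, 82 active and 28 placebo.

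**Step 1: reproduce the plan's own figures.** End of injection phase = last injection week + 12. Cohort 1: 5 + 12 = 17, 17 + 12 = 29, 29 + 12 = 41. These match the Weeks 17, 29 and 41 in 7.1.

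**Step 2: gap = 41 − end of injection phase.**

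| Last injection received | Cohort 1, 12 wk | Cohort 2, 8 wk | Cohort 2, 12 wk |
|---|---|---|---|
| 1st | 41 − 17 = 24 | 41 − 13 = 28 | 41 − 17 = 24 |
| 2nd | 41 − 29 = 12 | 41 − 17 = 24 | 41 − 21 = 20 |
| 3rd | 41 − 41 = 0 | 41 − 25 = 16 | 41 − 29 = 12 |
| 4th | – | 41 − 33 = 8 | 41 − 37 = 4 |
| 5th | – | 41 − 41 = 0 | 41 − 45 = −4 |

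The −4 is an overlap. Under the general 12-week rule, a Cohort 2 completer's injection phase runs to Week 45 while the tail has already begun at Week 41. With 8 weeks the two meet.

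**Step 3: classify one event under each rule.** Take a Grade 2 AE at Week 25 in a Cohort 1 participant who had only the Week 5 injection.

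| Rule | Result |
|---|---|
| 7.1, ITT periods | neither injection (ended Week 17) nor tail (starts Week 41) |
| 7.1, per-protocol tail | tail |
| 7.1, On-Treatment | counted |
| 9.5.5, primary endpoint | not counted |
| 9.5.5, 76-week and whole-study secondary endpoints | counted |
| Appendix algorithm | injection |
| SMC Weeks 5-41 tables | injection |

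A Week 35 event after two injections gives the same pattern. For a Cohort 1 completer with an event at Week 60, 7.1 gives tail and the appendix gives injection.

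**Step 4: size.** One participant who changes status moves a proportion by 1/n. In Cohort 1 this is 1/82 = 1.2 points on active and 1/28 = 3.6 points on placebo. It is slightly more if fewer were injected, and zero if the participant already has another qualifying event in the phase.

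The SAP gives no stopping rate and no event rate. As an illustration only, assume a fraction d of the 82 stop after one injection, and the Grade 2+ risk over Weeks 5-41 (36 weeks) is p with constant hazard h = −ln(1 − p)/36. The injection-phase proportion under a Weeks 5-41 rule then exceeds that under 7.1 by d × exp(−12h) × (1 − exp(−24h)).

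- d = 5%, p = 30%: 0.9 points (0.8 participants).
- d = 10%, p = 50%: 2.9 points (2.4 participants).
- d = 20%, p = 70%: 7.4 points (6.1 participants).

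**The case against.** The strongest reply is that nothing important is lost. On-Treatment contains every gap event, so part (d) of Tables 9-12 and 19 shows them. The 76-week and whole-study secondary endpoints count them, and Table 18 lists expedited and serious events whatever the phase. This stands: the loss is confined to parts (b) and (c).

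The appendix can also be read as meant only for the boundary at the first injection, since all its branches concern same-day events and missing onset days, with the end of the phase left to 7.1 and 9.5.5. That may be the intent, but the SAP does not say so, and the wording is open-ended. The SMC window may likewise be nominal, which is also unstated.

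A reader might infer more than the SAP supports:

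- **That the primary endpoint is biased by accident.** It is not. Section 9.5.5 sets its own window from the last injection, so leaving out a Week 25 event after a single Week 5 injection is the stated design.
- **That active-arm toxicity is understated.** This needs more early stopping on active, on which the SAP gives no figure.
- **That tail events would enter the injection count on active but not on placebo.** Section 4.3 follows placebo participants for 76 weeks after their last injection or until unblinding, whichever comes first, so Cohort 1 placebo participants may have substantial tail time.
- **That never-injected participants would be coded injection because of how software sorts missing dates.** This is a guess about unwritten code. The injectable safety population requires an injection, so they cannot enter the primary analysis. The missing branch in the algorithm still deserves a line.

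**Conclusion.** The point holds as an inconsistency in the by-phase safety tables. Section 7.1 leaves early stoppers with an interval in neither the injection nor the ITT tail phase: 24 or 12 weeks in Cohort 1, and in Cohort 2 between 4 and 28 weeks depending on the number of injections and on which window applies. The appendix and the SMC tables assign the same interval to the injection phase, and the appendix taken literally contradicts 9.5.5 for later events too.

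The week arithmetic rests only on the SAP's own schedule and definitions. The effect on reported proportions cannot be known from the SAP; the 1/82 and 1/28 steps show the sensitivity per participant, and the wider range depends on assumed stopping and event rates. Because the primary endpoint and the on-treatment summaries are unaffected once 9.5.5 and 7.1 are followed for them, this should be fixed before the phase tables are programmed, but it does not threaten the main conclusion.

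**What to change.** 1. In 7.1, set one injection-phase end date per cohort that agrees with 9.5.5: 12 weeks after the participant's last injection in Cohort 1 and 8 weeks in Cohort 2. Reconcile the general 12-week wording in 7.1 and the undifferentiated 12 weeks in 3.1 with it. This must come first: carrying over the per-protocol tail start while the 12-week rule remains would leave a 4-week overlap in Cohort 2.
2. For all safety tables, start the tail the day after that participant's injection-phase end date. Every gap and overlap in the table above then becomes zero.
3. Add the end date and a tail category to the appendix algorithm, and state that AEs of never-injected participants are never coded injection.
4. Use the same flags in the SMC tables, or label Weeks 5-41 there as a calendar window.

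The cost is SAP wording and one derived date in the AE program, with no new data. The downside is that tail time starts at different study weeks for early stoppers, which a table footnote should state.
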